Initially two cohorts of 10 patients with positive lymph nodes (as verified on postoperative histology) will be treated with different doses of 5-ALA. As lymph nodes can only be verified on post-operative histology it is anticipated that up to 16 patients may need to be treated to identify 10 with positive lymph nodes. As previously stated, we will attempt to enrich the study population to contain patients

Page | 31

with lymph node disease, but it is emphasised that this cannot be done accurately on preoperative CT staging. As a result, more than 10 patients may have to be recruited to each cohort to achieve the required 10 with positive lymph node disease. Sixteen patients per cohort have been anticipated as there is only 25% -30% lymph node positivity in colorectal cancer. With enrichment of recruitment, to include more lymph node positive patients using the FOxTROT radiology criteria, we estimate that 10 out of 16 patients will be informative with positive lymph nodes. In patients without lymph node disease, fluorescence of the primary cancer will act as a positive control of efficacy of 5-ALA FD of colorectal cancer. Table 1 below provides a guide to the doses that may be used. The two participating centres will work together in this regard, so as to co-ordinate between themselves, but the exact dose administered to each patient will be at the discretion of the treating surgeon. We will start with the predicted optimal dose of administration i.e. 20mg/kg (the most commonly used dose and timing in the literature – Appendix 1). A second cohort will be assessed at a lower dose of 10mg/kg if 20mg gives an indication of activity, or a higher dose of 30mg/kg if 20mg/kg does not give adequate indication of activity. In this way, by the time we have recruited 20 patients with positive lymph nodes we will have optimised the dose of administration.

Tabl	e 1
------	-----

Schedule	5-ALA dose
Cohort 1	20 mg/kg
Cohort 2	10 mg/kg or 30 mg/kg depending on activity
	of 5-ALA at 20 mg/kg

Information will be collected for each dose level including

- toxicity
- 5-ALA identified LN
- Histopathologically confirmed LN status

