Within the recruitment of the first 20 patients with positive lymph nodes, the ability of 5-ALA to detect positive nodes as compared to histology in at least 2 of 10 patients (in either cohort) will be required to progress to the next part of the study (see below). This corresponds to the upper bound of the 99% exact confidence interval of the sensitivity being at least 60% i.e. a good indication of activity given that the technical protocols and techniques may not yet be fully optimised. A 99% confidence interval has been chosen to reflect the additional uncertainty in 10 patients.

As the dose of 5-ALA is assessed, work will be carried out to standardise the preoperative radiological assessment, the technique of laparoscopic D3 lymphadenectomy and the pathological lymph node mapping.

If 5-ALA detects positive lymph nodes in at least 2 of 10 patients (in either cohort) then, from these initial results, the most promising dose of 5-ALA will be identified. Both patient and node-level information and practical considerations will be used to further inform this decision. At least a further 10 patients with lymph nodes with metastatic disease as judged by histological evaluation will then be recruited and treated with this schedule, with flexibility to include further patients to confirm the validity of the technique before proceeding to the evaluation phase. The exact number of patients will be determined in discussion with the TSC and DMEC prior to the start of this stage of the trial but, at their discretion, may be increased during this stage of the trial. We will aim to recruit up to 52 patients in total for the developmental phase. However, if necessary, more than this number of patients will be recruited to obtain this number with metastatic disease as judged by histological evaluation. The ability of 5-ALA FD to reliably detect lymph nodes with metastatic disease as judged by histopathological evaluation will be assessed by requiring that, to progress to the evaluation phase, the upper bound of the 99% (Clopper Pearson) confidence interval of the sensitivity (in the patients with positive nodes recruited in this stage of the trial) is at least the target value of 80%. This analysis will be versus histopathology but on a per patient basis, considering whether a patient has at least

1 node identified by 5-ALA. A 99% confidence interval has been used to reflect the additional uncertainty in a relatively low number of patients.

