15. ENDPOINTS

15.1 Primary Endpoints

 Identification of the optimal dose for oral administration of 5-ALA for the accurate intraoperative detection of lymph node metastases

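### The protocol says the dose will have been optimised after two cohorts of 10, but the design supports only a provisional selection

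*Protocol*

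**What the plan says.** Protocol 8.1 (Study Design) begins with "Initially two cohorts of 10 patients with positive lymph nodes". The first cohort receives 20 mg/kg. The second receives 10 or 30 mg/kg, depending on the activity seen in the first: "A second cohort will be assessed at a lower dose of 10mg/kg if 20mg gives an indication of activity", and the higher dose otherwise. The paragraph concludes that "by the time we have recruited 20 patients with positive lymph nodes we will have optimised the dose of administration". The synopsis repeats this sentence. Section 15.1 gives one primary endpoint: "Identification of the optimal dose for oral administration of 5-ALA for the accurate intraoperative detection of lymph node metastases".

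The operative rule comes later in 8.1 and again in 17.1: "If 5-ALA detects positive lymph nodes in at least 2 of 10 patients (in either cohort) then, from these initial results, the most promising dose" is identified. On the basis of that threshold, 8.1 says: "This corresponds to the upper bound of the 99% exact confidence interval of the sensitivity being at least 60" per cent. On how the dose is chosen, it says: "Both patient and node-level information and practical considerations will be used to further inform this decision". At least 10 further node-positive patients are then treated at the chosen dose. Section 17 makes the analysis of the section 15 endpoints descriptive.

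**The concern.** The protocol uses two descriptions of the same result. One is a dose that is optimised or optimal (synopsis, 8.1, 15.1). The other is a dose that looks most promising and goes forward (8.1, 17.1). The first claims a comparative property, that the dose is better than, or at least as good as, the alternatives. The second is a selection.

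Once the 2-of-10 requirement is met, a dose is always named, and 8.1 has already said that it will be the optimised one. Section 8.1 also says that the findings feed directly into the protocol of the multicentre evaluation phase. What is at stake is the claim carried forward: the trial could report that its primary endpoint was met with an optimal dose when the data show only that one dose was active and was picked.

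**Working it through.** **1. The plan's own threshold.** The upper limit of a two-sided 99% Clopper-Pearson interval for x of n is the 0.995 quantile of Beta(x+1, n−x). With n = 10:

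- x = 1: 54.4%
- x = 2: 64.8%

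So 2 is the smallest count whose upper limit reaches 60%, and the stated figure is reproduced. The calculation concerns one cohort at a time and contains no comparison between doses.

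**2. How easily the threshold is passed.** Let P = Pr(X ≥ 2) for X ~ Binomial(10, p). If both doses have sensitivity p, at least one cohort passes with probability 1 − (1 − P)².

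| True sensitivity at both doses (assumed) | P | At least one cohort passes |
|---|---|---|
| 10% | 0.264 | 46% |
| 20% | 0.624 | 86% |
| 30% | 0.851 | 98% |
| 40% | 0.954 | above 99% |

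Passing therefore says little about which dose is better.

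**3. What 10 v 10 says about the ranking.** The documents give no true sensitivity for any dose, so the values below are assumptions. 80% and 60% are the reference values used in 8.1 for the two progression rules. With independent counts A ~ Binomial(10, p₁) for the worse dose and B ~ Binomial(10, p₂) for the better, sum Pr(A = a)·Pr(B = b) over b > a, b = a and b < a.

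| Assumed sensitivities | Better dose leads | Tie | Worse dose leads |
|---|---|---|---|
| 80% v 70% | 60.4% | 18.0% | 21.6% |
| 80% v 60% | 77.6% | 11.9% | 10.5% |
| 60% v 40% | 75.5% | 11.7% | 12.8% |
| 80% v 40% | 95.6% | 2.9% | 1.5% |

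If both doses are truly 80%, the counts tie in 22.4% of trials, so one cohort appears ahead in 100 − 22.4 = 77.6%.

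**4. Precision of an observed difference.** Newcombe's 95% interval for d = p̂₂ − p̂₁ combines the Wilson limits (l, u) of each cohort: lower = d − √[(p̂₂ − l₂)² + (u₁ − p̂₁)²]; upper = d + √[(u₂ − p̂₂)² + (p̂₁ − l₁)²].

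For 8/10 v 6/10 the Wilson limits are 0.490 to 0.943 and 0.313 to 0.832:

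- lower = 0.20 − √(0.310² + 0.232²) = −0.19
- upper = 0.20 + √(0.143² + 0.287²) = +0.52

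The same method gives −2 to +67 points for 8/10 v 4/10, and −37 to +37 points for 5/10 v 5/10. Equal counts would therefore not show that a lower dose keeps the activity of a higher one.

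**5. Features that counts do not capture.** The second cohort follows the first, and 8.1 accepts that technique may not be fully developed during this stage. It leaves patients treated before the dose was selected out of the later analysis for that reason. Any difference between cohorts thus mixes dose with growing experience. Sections 8.1 and 12.4 list three doses, but the initial cohorts cover two. The later stage has no second dose to compare with.

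**The case against.** The strongest reply is that this is a descriptive development study that picks a dose and then tests it. The action taken in 8.1 and 17.1 is to identify the most promising dose, from the results and with node-level and practical information. Toxicity is collected at each dose level. At least 10 new patients follow before the evaluation phase. If neither cohort reaches 2 of 10, the study does not progress. Picking a winner with 10 per dose is a legitimate design, and low power for a formal comparison is not an error in it.

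All of that stands, and it rules out three stronger readings that a reader might infer.

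- That 10 v 10 cannot tell doses apart at all. It can when the gap is large: 80% v 40% is ranked correctly in 96% of trials.
- That the same dose is chosen whatever the results. The wording fixes that a dose will be named, not which one.
- That 22% is the chance of choosing the worse dose. It describes patient counts alone, and 8.1 brings in other information. Where two doses are truly equal, choosing either loses no sensitivity.

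The reply does not defend the unconditional claim. The later stage checks the sensitivity of the chosen dose but never sets it against the other, and a sound selection design still yields a selected dose rather than an optimum.

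**Conclusion.** The point holds as one about what the trial may conclude. The statement in 8.1 and the synopsis that the dose will have been optimised, and the word *optimal* in 15.1, go beyond a design whose only stated criterion is activity in either cohort and which provides no outcome for doses that are not distinguished.

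In size: for assumed true differences of 10 to 20 points, patient counts put the better dose ahead in 60% to 78% of trials, and only gaps of about 40 points are ranked reliably. This rests on assumed sensitivities, independent patients and patient counts alone. It does not show that the selection design is wrong or that any particular dose is wrong. The absence of a detailed comparison method is not a fault either, since section 17 commits to a full analysis plan before any analysis.

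**What to change.** Reconcile the two descriptions. In the synopsis, 8.1 and 15.1, replace the claim of an optimised or optimal dose with a dose selected for further confirmation, in line with the *most promising* wording already in 8.1 and 17.1.

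Report, descriptively, each initial cohort's per-patient sensitivity with an exact interval, and the between-cohort difference with its interval. State alongside them that the cohorts were sequential and that not all listed doses were studied. The conclusion should then claim no more than those figures show. The interval is there to convey uncertainty; it is not a significance test and not a criterion for choosing. No dose and no dose-selection rule is proposed.

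The cost is a wording amendment in three places and a small summary of data already collected, with no extra patients. The downside is a less favourable claim about the dose.

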7 AIMS AND OBJECTIVES

The purpose of this study is to optimise the use of 5-ALA for intra-operative fluorescence diagnosis (FD) of metastatic lymph nodes in colon cancer. We hypothesize that 5-ALA FD provides an accurate means of intraoperative lymph node staging and that it is more accurate than preoperative CT staging.

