17.1 Frequency of analyses

See Section 8.1 for details of the study design.

Within the recruitment of the first 20 patients with positive lymph nodes, the ability of 5-ALA to detect positive nodes as compared to histology in at least 2 of 10 patients (in either cohort) will be required to progress to the next part of the study.

If 5-ALA detects positive lymph nodes in at least 2 of 10 patients (in either cohort) then, from these initial results, the most promising dose of 5-ALA will be identified. At least a further 10 patients with lymph nodes with metastatic disease as judged by histological evaluation will then be recruited and treated with this schedule, with flexibility to include further patients to confirm the validity of the technique before proceeding to the evaluation phase. The ability of 5-ALA FD to reliably detect lymph nodes with metastatic disease as judged by histopathological evaluation will be assessed by requiring that, to progress to the evaluation phase, the upper bound of the 99% (Clopper-Pearson) confidence interval of the sensitivity (in the patients with positive nodes recruited in this stage of the trial) is at least the target value of 80%. To allow for the optimization of the other variables (e.g. fluorescence detection), however, this analysis will not include patients treated with this schedule before it was identified as the most promising schedule.

Safety will be assessed on an ongoing basis. Particular attention will be paid to the rates of conversion, resection margin positivity and post-operative outcomes of laparoscopic segmental colectomy with D3 lymphadenectomy as markers of safety. Any rates deemed to be excessive (e.g. conversion rates >50%; resection margin positivity >30%; morbidity >50%; anastomotic leak rates ≥10%; major complication

rate \geq 30%; re-operation rate \geq 10%, 30-day mortality rate \geq 5%) will prompt further investigation and, if necessary, the suspension or withdrawal of individual sites or termination of the entire trial. Adverse events suspected to be related to 5-ALA will be reviewed in real time by the DMEC. Serious adverse events (SAEs) not suspected to be related to 5-ALA will also be reviewed in real time by the DMEC

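### The progression rules show only that 60% and 80% sensitivity have not been excluded, but the protocol presents them as evidence of activity and of reliable detection

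*Protocol*

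**What the plan says.** Section 8.1 sets two numerical rules.

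- **First stage.** At least 2 of 10 node-positive patients, in either dose cohort, must have positive nodes detected. Section 8.1 and the synopsis equate this with "the upper bound of the 99% exact confidence interval of the sensitivity being at least 60% i.e. a good indication of activity", allowing that the techniques may not yet be fully optimised.
- **Second stage.** "At least a further 10 patients with lymph nodes with metastatic disease as judged by histological evaluation will then be recruited". The exact number is agreed with the TSC and DMEC beforehand and may be increased during the stage. The requirement is that, "to progress to the evaluation phase, the upper bound of the 99% (Clopper Pearson) confidence interval of the sensitivity" "is at least the target value of 80"%, judged per patient.

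The second rule is introduced with "The ability of 5-ALA FD to reliably detect lymph nodes with metastatic disease as judged by histopathological evaluation will be assessed by requiring" it, and section 17.1 repeats the claim: "The ability of 5-ALA FD to reliably detect lymph nodes with metastatic disease as judged by histopathological evaluation". The reason given for 99% (section 8.1 and synopsis) is the extra uncertainty that comes with few patients. No minimum count, point estimate or lower limit is stated for the second rule. On size, "We will aim to recruit up to 52 patients in total for the developmental phase".

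**The concern.** An upper confidence limit at or above a target says that the data are compatible with the target. It does not say that the target, or anything near it, has been reached. A rule of this kind can justify stopping when it fails. It cannot support a statement about reliability when it passes.

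This is the only numerical efficacy condition stated for entry to the multicentre evaluation phase. Read as written, a trial in which 6 of 10 node-positive patients were missed could be reported as having met its test of reliable detection.

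The stated reason for 99% compounds this. A reader would expect a higher level, chosen because of uncertainty, to make a claim harder to earn. On an upper bound it does the opposite.

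**Working it through.** **Inputs**
- Targets 60% (first rule) and 80% (second rule), level 99%, exact interval: section 8.1.
- Minimum n = 10 node-positive patients: section 8.1.
- Implied n: 52 in total, less two cohorts of 16, leaves 52 − 32 = 20 treated. At the protocol's expected yield of 10 in 16, that is 20 × 10/16 = 12.5, so 12 or 13 node-positive.
- Two-sided interval assumed (0.5% per tail), since the protocol does not say; one-sided checked.

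**Formulas**
- Upper limit for x of n: the 1 − α/2 quantile of Beta(x + 1, n − x). Lower limit: the α/2 quantile of Beta(x, n − x + 1).
- Pass probability with minimum count m and true sensitivity p: the sum over k from m to n of C(n,k) p^k (1 − p)^(n−k).

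**Step 1. The protocol's own figure.** At n = 10, 1/10 has an upper limit of 54.4% and 2/10 has 64.8%. The minimum for 60% is therefore 2, as stated (one-sided: 50.4% and 61.2%, same minimum). The lower limit for 2/10 is 1.1%.

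**Step 2. The second rule at n = 10.** 3/10 has an upper limit of 73.5% and fails. 4/10 has the interval 7.7% to 80.9% and passes. One-sided, 4/10 gives 78.2% and fails, so 5/10 is needed.

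**Step 3. Pass probabilities at n = 10, m = 4**
- True 50%: 1 − (1 + 10 + 45 + 120)/1024 = 848/1024 = 82.8%.
- True 40%: 1 − (0.0060 + 0.0403 + 0.1209 + 0.2150) = 61.8%.

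The same calculation for other n, two-sided 99%:

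| n | Minimum | Observed rate needed | Pass at true 40% | at 50% | at 60% | at 80% |
|---|---|---|---|---|---|---|
| 10 | 4 | 40% | 62% | 83% | 95% | 99.9% |
| 12 | 6 | 50% | 33% | 61% | 84% | 99.6% |
| 13 | 6 | 46% | 43% | 71% | 90% | 99.9% |
| 15 | 8 | 53% | 21% | 50% | 79% | 99.6% |
| 20 | 11 | 55% | 13% | 41% | 76% | 99.7% |

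One-sided minima are 5/10, 6/12, 7/13, 8/15 and 12/20. At 5/10 the pass probability at true 50% is 62%.

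**Step 4. Effect of the level.** At two-sided 95% and n = 10:
- First rule: 2/10 has an upper limit of 55.6% (fail) and 3/10 has 65.2% (pass).
- Second rule: 4/10 has 73.8% (fail) and 5/10 has 81.3% (pass).

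Moving from 95% to 99% therefore lowers the bars from 3 to 2 and from 5 to 4.

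**Step 5. Effect of n.** The observed rate needed tends to fall as n gets smaller (55% at 20, 40% at 10), though not at every step (50% at 12, 46% at 13).

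**Step 6. First rule with two chances.** One cohort passes with probability 26.4% at true 10% and 62.4% at true 20%. If both doses had the same true sensitivity and the cohorts were independent, at least one passes with probability 1 − (1 − 0.264)² = 46% and 1 − (1 − 0.624)² = 86%. Equal sensitivity at the two doses is an assumption made here for scale.

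**The case against.** The strongest defence is that a lenient screen suits a developmental phase. The synopsis leaves sensitivity, specificity and diagnostic accuracy to the later evaluation phase, section 17 calls the analysis descriptive, and section 8.1 concedes that the techniques may not yet be optimised. For a rule meant to avoid abandoning a promising technique too early, a wide interval at small n is coherent: the less is known, the more failure is needed before stopping. All of this stands. It shows that the rule can be kept. It does not rescue the description of what a pass demonstrates, or the stated reason for 99% as support for that description.

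A reader might go further and infer that a technique less sensitive than CT would usually be sent forward. The documents do not support that, for three reasons.

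- The bound is something required in order to progress. Nothing says that meeting it obliges progression, so the figures above are probabilities of meeting one condition.
- The word *usually* depends on n and on the true value. At n = 10 the rule is met 35% of the time at true 30%. At n = 12 to 13 it is met only 33% to 43% of the time at true 40%.
- The CT sensitivities in section 6.3 (64% and 70%) come from other studies, whereas this trial enriches for advanced tumours and scores each patient on a single node. Section 7 hypothesises that "it is more accurate than preoperative CT staging", which concerns accuracy, and no section makes beating CT a condition for progression. The comparison is indicative at most.

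**Conclusion.** The rules are usable as futility screens and wrongly described as more. A pass on the second rule means that 80% is not excluded; a pass on the first means that 60% is not excluded. At the minimum n of 10, 4/10 suffices, with pass probability 62% at true 40% and 83% at true 50%. At the 12 to 13 node-positive patients implied by the recruitment total, the minimum is 6 and the probabilities are 33% to 43% and 61% to 71%.

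These figures rest on a two-sided 99% Clopper-Pearson interval and on the protocol's yield of 10 in 16. A one-sided bound raises the minimum at n = 10 to 5 and leaves the conclusion unchanged. The CT comparison is not needed for it.

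**What to change.** 1. In section 8.1, section 17.1 and the synopsis, describe both rules as futility screens (60% not excluded; 80% not excluded) that are necessary but not sufficient for progression.
2. State whether the bound is one- or two-sided. Print the minimum counts for the final rule (two-sided: 4/10, 6/12, 6/13, 8/15, 11/20) with their pass probabilities, so that the TSC and DMEC can see what bar each choice of n sets.
3. Remove reliable detection as the description of what the second rule assesses (all three places), and remove the claim of good activity from the first (section 8.1 and synopsis).
4. Replace the reason for 99% (section 8.1 and synopsis) with the true one: a low risk of stopping a technique that meets the target. At true 80% that risk is 0.1% at n = 10 and 0.3% at n = 20.

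The cost is wording only, with no extra patients.

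A positive criterion is an option for the sponsor, TSC and DMEC to weigh, not a required correction. An observed sensitivity of at least 70%, for example, passes at true 50% in 17% of trials (7/10) or 5.8% (14/20). It would, however, stop a technique with true 80% sensitivity in 12% or 9% of trials. It still passes 49% or 38% of the time at true 64%, so it does not establish superiority to CT. The n = 20 version also needs about 20 × 16/10 = 32 patients treated in that stage, so 32 + 32 = 64 in all against the planned 52.

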As the dose of 5-ALA is assessed, work will be carried out to standardise the pre-operative radiological assessment, the technique of laparoscopic D3 lymphadenectomy, and the pathological lymph node mapping.

If 5-ALA detects positive lymph nodes in at least 2 of 10 patients (in either cohort) then, from these initial results, the most promising dose of 5-ALA will be identified. At least a further 10 patients with lymph nodes with metastatic disease as judged by histological evaluation will then be recruited and treated with this schedule, with flexibility to include further patients to confirm the validity of the technique before proceeding to the evaluation phase. The exact number of patients will be determined in discussion with the TSC and DMEC prior to the start of this stage of the trial but, at their discretion, may be increased during this stage of the trial. We will aim to recruit up to 52 patients in total for the developmental phase. However, if necessary, more than this number of patients will be recruited to obtain this number with metastatic disease as judged by histological evaluation. The ability of 5-ALA FD to reliably detect lymph nodes with metastatic disease as judged by histopathological evaluation will be assessed by requiring

	that, to progress to the evaluation phase, the upper bound of the 99% (Clopper Pearson) confidence interval of the sensitivity (in the patients with positive nodes recruited in this stage of the trial) is at least the target value of 80%. This analysis will be versus histopathology but on a per patient basis, considering whether a patient has at least 1 positive tumour node identified by 5-ALA. A 99% confidence interval has been
	used to reflect the additional uncertainty in a relatively low number of patients. To allow for the optimization of the other variables (e.g. fluorescence detection system), however, this analysis will not include patients treated with this schedule before it was identified as the most promising schedule.
Trial Population	Adult patients undergoing elective surgery for colon adenocarcinoma
Inclusion Criteria	 Patients undergoing elective surgery for right or sigmoid colon cancer amenable to laparoscopic surgery incorporating D3 lymphadenectomy, including those with metastatic disease. American Society of Anaesthesiologists (ASA) classification ≤ 3 Normal hepatic and renal function

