16. STATISTICAL CONSIDERATIONS

16.1 Sample size

See Section 8.1 (study design).

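### The synopsis and Section 8.1 define a detected patient differently for the stage 2 go/no-go sensitivity, and the Section 8.1 wording can only push it upward

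*Protocol*

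**What the plan says.** The developmental phase has two decision points. Stage 1 requires that 5-ALA detect histologically positive nodes in at least 2 of 10 node-positive patients in either dose cohort. Stage 2 then recruits "At least a further 10 patients with lymph nodes with metastatic disease as judged by histological evaluation" at the chosen dose. To progress to the evaluation phase, "the upper bound of the 99% (Clopper Pearson) confidence interval of the sensitivity", calculated "in the patients with positive nodes recruited in this stage of the trial", must meet the condition that it "is at least the target value of 80" per cent.

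The stage 2 analysis is described in two places in nearly the same words, but the counting rule differs:

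- Synopsis (Section 3, Trial Design): "considering whether a patient has at least 1 positive tumour node identified by 5-ALA".
- Section 8.1: the patient needs at least "1 node identified by 5-ALA". The words requiring the node to be a positive tumour node are absent.

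Section 8.1 also says: "This analysis will be versus histopathology but on a per patient basis". Section 16.1 sends the reader to 8.1 for sample size ("See Section 8.1 (study design"), and Section 17.1 refers to 8.1 for the design. Section 17.1 restates the 99% interval and the 80% target but does not say what makes a patient a success.

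**The concern.** The two rules classify one kind of patient differently: a node-positive patient whose metastatic nodes all failed to fluoresce but who had at least one fluorescent node free of tumour. Under the synopsis this patient is a false negative. Under the literal 8.1 wording the patient is a detection.

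The reference to histopathology does not settle the matter. The denominator is already limited to patients who are node-positive on histology. A patient-level comparison (any fluorescence, yes or no, against histology positive, yes or no) would satisfy that phrase without the fluorescent node being the involved one.

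Every patient who succeeds under the synopsis rule also succeeds under the 8.1 rule, so the 8.1 count can never be the smaller. Any error therefore favours progression. The criterion tests only an upper confidence bound on sensitivity and has no specificity component, so the criterion itself would not reveal the problem.

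**Working it through.** **Reproducing the protocol's own figure.** The two-sided 99% Clopper–Pearson upper bound for x successes in n is the 0.995 quantile of a Beta(x+1, n−x) distribution. For stage 1 with n = 10, x = 1 gives 54.4% and x = 2 gives 64.8%. Two is therefore the smallest count whose upper bound reaches 60%, as the protocol states.

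**Pass mark at stage 2.** With n = 10, the stated minimum, x = 3 gives 73.5% and x = 4 gives 80.9%. At least 4 of 10 are needed. The pass mark is the same under both wordings; what changes is who is counted.

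**One patient can decide it.** Take three patients with a fluorescent involved node and a fourth with only a fluorescent benign node. The synopsis rule gives 3 of 10 (73.5%, criterion not met). The literal 8.1 rule gives 4 of 10 (80.9%, criterion met).

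**Effect on the chance of meeting the criterion.** Let s be the true per-patient sensitivity under the synopsis rule. Let f be the chance that a node-positive patient whose involved nodes were all missed has at least one fluorescent benign node. The proportion counted under the literal 8.1 rule is

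q = s + (1 − s) × f,

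and the chance of meeting the criterion is P(X ≥ 4) with X binomial(10, q). The protocol gives no value for f, so a range is shown. The column f = 0 is the synopsis rule.

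| True s | f = 0 | f = 0.1 | f = 0.2 | f = 0.3 |
|---|---|---|---|---|
| 0.1 | 0.013 | 0.104 | 0.298 | 0.540 |
| 0.2 | 0.121 | 0.298 | 0.513 | 0.712 |
| 0.3 | 0.350 | 0.540 | 0.712 | 0.844 |
| 0.4 | 0.618 | 0.755 | 0.859 | 0.929 |

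For s = 0.2 the values of q are 0.20, then 0.2 + 0.8 × 0.1 = 0.28, 0.2 + 0.8 × 0.2 = 0.36 and 0.2 + 0.8 × 0.3 = 0.44.

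**A larger stage 2.** Ten is a minimum. With n = 20 the pass mark is 11 (upper bound 81.9%; 10 of 20 gives 78.2%). At s = 0.2 the chances are then 0.001, 0.010, 0.065 and 0.221 for f = 0, 0.1, 0.2 and 0.3. At s = 0.4 they are 0.128, 0.279, 0.483 and 0.694. A larger sample lowers the chance of passing at these sensitivities but does not remove the bias.

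**The case against.** The strongest reply is that this is a drafting slip. In 8.1 the sentence just before the counting rule gives the purpose as reliable detection of nodes with metastatic disease, Section 17.1 repeats that purpose, and the synopsis spells the rule out. This stands as evidence of intent: the synopsis meaning was probably meant. It does not remove the mismatch, because the counting sentence in the body of the protocol omits the condition.

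A second reply is that the operational definition belongs in the statistical analysis plan, which Section 17 requires before any analysis and which is not shown here. That would be an answer if the protocol were silent. Instead it states two rules, and any such plan would have to depart from the wording of one of them.

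A third reply is that the 80% criterion is a requirement for progression and is not described as sufficient. Stage 2 size is set with the steering and monitoring committees, and Appendix 3 has a final report relating involved nodes to fluorescent ones. Fluorescence confined to benign nodes would therefore be visible to a careful reader. That is fair, and it limits the practical risk, but the formal criterion would still be computed from the wrong count.

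A reader might also infer more than the documents support:

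- *That a dye with no true detection could reach the evaluation phase.* The stage 1 rule is worded as detecting positive nodes against histology. Such a dye would score 0 of 10 in both cohorts and stop there.
- *That the stage 1 rule has the same fault.* It does not.
- *That false positives would dominate the numerator because a specimen holds many benign nodes.* The 27-node table in Appendix 3 only illustrates how to fill in the form. Its example patient has a fluorescent involved node and so succeeds under both rules. Fluorescence is read at initial laparoscopy, so the number of benign nodes at risk is unknown. The 78% node-level specificity cited in Section 6.4 is for fluorescence without exogenous 5-ALA and cannot stand in for the missing rate.

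**Conclusion.** The concern holds as an inconsistency in the definition of the quantity that gates the evaluation phase. The synopsis and Section 8.1 give different numerators, Section 17.1 does not choose between them, and the literal 8.1 rule can only bias the stage 2 sensitivity upward. The false positives at issue are benign nodes within node-positive patients; node-negative patients are not in the denominator.

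The direction of the bias is certain; its size is not. The rise from 12% to about 30%, 51% and 71% rests on four assumptions: 10 patients, a true per-patient sensitivity of 20%, independent patients, and a fluorescent benign node in 10%, 20% or 30% of missed patients. None of those percentages comes from the protocol. If benign nodes never fluoresce in missed patients, the two rules give the same answer.

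The wording should be reconciled before the stage 2 data are read. The conflict does not undermine the design, the stage 1 gate or the 4-of-10 pass mark.

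**What to change.** Align Section 8.1 with the synopsis and repeat the definition in Section 17.1. Suggested text: *A node-positive patient is a true positive only if at least one node marked fluorescent at operation contains metastasis on final histology. A node-positive patient whose only fluorescent nodes are histologically negative is a false negative.*

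Leave the stage 1 rule as it stands.

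The cost is this short definition in two places. The sample size, the interval and the target do not change. The data are already planned: fluorescent nodes are clipped at operation (Section 11.2), and each is blocked individually and reported against its histology (Appendix 3).
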